Appendix L Visit windows

Part A

Visit Number	Visit Type	Lower Allowable Window	Lower Target Day	Target Day	Upper Target Day	Upper Allowable Window
01.0	Screening	-56	-		-	-
02.0	Enrollment¹ Infusion	-	-	0	-	-
03.0	3 days post infusion	-1	-	3	-	+1
04.0	6 days post infusion	-1	-	6	-	+2
05.0	4 weeks post infusion	-7	-3	28	+3	+7
06.0	8 weeks post infusion	-7	-3	56	+3	+7
07.0	16 weeks post infusion	-7	-3	112	+3	+7
08.0						
09.0	24 weeks post infusion	-7	-3	168	+3	+7

Greyed-out visit does not apply to Part A.

Part B

Visit Number	Visit Type	Lower Allowable Window	Lower Target Day	Target Day	Upper Target Day	Upper Allowable Window
01.0	Screening	-56	-		-	-
02.0	Enrollment Infusion #1	-	-	0	-	-
03.0	3 days post infusion #1	-1	-	3	-	+1
04.0	6 days post infusion #1	-1	-	6	-	+2
05.0	4 weeks post infusion #1	-7	-3	28	+3	+7
06.0	8 weeks post infusion #1	-7	-3	56	+3	+7
07.0	Infusion #2	-14	-7	112	+7	+14
08.0	4 days post infusion #2	-	-	116	+7	-
09.0	8 weeks post infusion #2	-7	-3	168	+3	+7
10.0	16 weeks post infusion #2	-7	-3	224	+3	+7
11.0	24 weeks post infusion #2	-7	-3	280	+3	+7

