6.4 Statistical analyses

This section describes the final study analyses, unblinded as to treatment arm assignment. All safety data from enrolled participants will be analyzed according to the initial randomization assignment regardless of how many study product administrations and how much study product they received. In the rare instance that a participant receives the wrong treatment at a specific study product administration time, the Statistical Analysis Plan (SAP) will address how to analyze the participant's safety data. Analyses of safety data are modified intent-to-treat (MITT) in that individuals who are randomized but not enrolled do not contribute data and hence are excluded. Because of the brief length of time between randomization and enrollment—typically no more than 4 working days—very few such individuals are expected. The primary analysis of mAb concentration and anti-viral functional activity data are per-protocol (PP) in that only individuals who receive the expected mAb at the expected dose level within the expected visit window contribute data. Secondary analysis will also involve the MITT cohort, and when necessary account for the actual specimen collection time, and the actual time and dose amount of each product administration.

Analyses for primary endpoints will be performed using SAS and R. Additional software may be used to perform non-compartmental PK and population PK analyses (eg, Monolix). All other descriptive and inferential statistical analyses will be performed using SAS, StatXact, or R statistical software.

No formal multiple comparison adjustments will be employed for multiple primary or secondary endpoints. However, multiplicity adjustments will be made for certain primary or secondary endpoint assays, as discussed below, when the assay endpoint is viewed as a collection of hypotheses (eg, testing multiple pseudo-viruses to determine a positive antiviral functional activity response). Unless otherwise noted, all statistical tests will be 2-sided and will be considered statistically significant if $p < 0.05$.

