6.4.4.1 Primary analyses of mAb concentrations

The primary analysis of serum concentration and PK of PGDM1400LS, VRC07-523LS and PGT121.414.LS (Primary Objective 2) will be restricted to participants who received all scheduled administrations per-protocol. Serum concentrations that fail the quality control of the assay, or from specimens collected outside of the visit window, or from HIV-infected participants postinfection may be excluded. The primary analysis of serum concentration will be descriptive and performed separately for each mAb.

A non-compartmental PK analysis will be performed on the concentration data. PK parameters may include, but are not limited to: area-under-the-curve (AUC), maximum concentration (C_{max}), time to C_{max} (T_{max}), clearance (CL), volume of distribution (Vd), terminal elimination rate constant (λ_z) and the terminal half-life ($T_{1/2}$). For SC Groups, the PK parameters will include AUC, C_{max} , T_{max} , clearance (CL/F, where F is the bioavailability via SC relative to IV), volume of distribution (Vd/F), λ_z and $T_{1/2}$. Data will be summarized by each dose group and overall for CL, Vd and $T_{1/2}$. The potential for non-linear PK among IV or SC recipients will be determined by comparing the dose-adjusted ratios for C_{max} and AUC within IV or SC dosing groups. Graphical displays of the data (eg, boxplots, scatterplots, histograms, spaghetti plots) will be generated to visually explore distributional properties of the data. These summary statistics and graphical displays may be produced for each treatment arm and each time point separately.

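### Part B visits after infusion #2 are labelled by time since that infusion, but their windows are listed on the infusion #1 day scale with no stated anchor, so the 8-week sample can fall 35 to 77 days after the dose

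*Protocol*

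**What the plan says.** The Part B table in Protocol Appendix L sets Day 0 at "Enrollment Infusion #1". The row for the second dose reads "07.0 Infusion #2 -14 -7 112 +7 +14", so its allowable days are 98 to 126 and its target days 105 to 119. The visits that follow are named by time since that dose but carry target days on the same scale. Visit 9, for example, is labelled "8 weeks post infusion #2", and its full row reads "09.0 8 weeks post infusion #2 -7 -3 168 +3 +7". Visits 10 and 11, labelled 16 and 24 weeks, have target Days 224 and 280, each ±7. Visit 8, "4 days post infusion #2", has target Day 116, an upper target of +7 and no allowable limits. Appendix I heads Visits 9 to 11 as D168/W24, D224/W32 and D280/W40, weeks that count from enrollment.

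Two analysis rules refer to visit windows. Protocol Section 6.4.4.1 lists, among concentrations that may be left out of the primary analysis, those that fail assay quality control "or from specimens collected outside of the visit window". Protocol Section 6.4, repeated in SAP Section 8, defines the per-protocol set so that "only individuals who receive the expected mAb at the expected dose level within the expected visit window contribute data". Protocol Section 4.1 says that participants are followed for 24 weeks after their last dose.

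**The concern.** Label and target day agree only if infusion #2 is given on Day 112. On any other allowed day the two columns describe different dates, and neither document says which one governs. Primary endpoints 2 and 3 are measured at prespecified times, and Protocol Section 6.1.2 describes the concentration objective as estimating group means at set times after dosing, with 12 evaluable participants assumed per group. A site or database that follows the target-day column would accept a 35-day sample as the 8-week value and flag a 56-day sample as out of window. Delays to the second dose are foreseeable: Section 7.3.1 lists several reasons for them.

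**Working it through.** **Inputs.** Infusion #2 on Days 98–126 (target window 105–119); Visits 9, 10 and 11 at Days 168, 224 and 280, each ±7 (all Appendix L). Half-life of 38 days for IV VRC07-523LS (Protocol Section 4.8.4). Planning log SD 0.5 and n = 12 (Section 6.1.2). The 60-day half-life used below is an assumption, included to show a range.

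**1. Nominal labels.** Target day minus 112 gives 116 − 112 = 4, 168 − 112 = 56, 224 − 112 = 112 and 280 − 112 = 168 days. These reproduce the labels of 4 days and 8, 16 and 24 weeks.

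**2. Allowed time since infusion #2, windows read from Day 0.** Earliest = lower limit − 126; latest = upper limit − 98.

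| Visit | Label (days) | In-window days | Earliest | Latest | Range if infusion #2 is on Days 105–119 |
|---|---|---|---|---|---|
| 9 | 56 | 161–175 | 161 − 126 = 35 | 175 − 98 = 77 | 42–70 |
| 10 | 112 | 217–231 | 217 − 126 = 91 | 231 − 98 = 133 | 98–126 |
| 11 | 168 | 273–287 | 273 − 126 = 147 | 287 − 98 = 189 | 154–182 |

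**3. Samples at exactly the labelled interval.** With infusion #2 on day d, a 56-day sample is in window if 161 ≤ d + 56 ≤ 175, that is, 105 ≤ d ≤ 119. Visits 10 and 11 give the same limits (217 − 112 = 105 and 231 − 112 = 119; 273 − 168 = 105 and 287 − 168 = 119). The exact-interval sample is therefore out of window for d = 98–104 and d = 120–126, which is 14 of the 29 allowable days. This is a count of days, not a probability.

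**4. The 24-week follow-up.** The last in-window day for Visit 11 is 287. For infusions on Days 120 to 126 that is 287 − 120 = 167 down to 287 − 126 = 161 days, short of 168. The follow-up stated in Section 4.1 cannot then be reached within the window.

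**5. Visit 8.** Its Day 116 target falls before the infusion whenever infusion #2 is on Days 117–126.

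**6. Size of the timing effect.** Assuming exponential decline with a 38-day half-life, the two ends of the Visit 9 range differ by 2^(42/38) = 2.15-fold; at 60 days, 2^(42/60) = 1.62-fold. These compare opposite extremes. For the typical effect, assume that infusion day and visit day are independent and uniform over their allowable windows. The variance of the interval is 28²/12 + 14²/12 = 81.7, so the SD is 9.0 days. On the log scale this is 9.0 × 0.693/38 = 0.16 to 0.17 (0.10 at 60 days). Independent variation adds in quadrature: √(0.5² + 0.165²) = 0.53, or 0.51 at 60 days. The example interval in Section 6.1.2, (7.3, 13.7), becomes about (7.2, 14.0).

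**7. After re-anchoring.** With the same ±7 days counted from the actual infusion #2, Visit 9 spans 49–63 days, Visit 10 spans 105–119 and Visit 11 spans 161–175. An exact-interval sample is then always in window.

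**The case against.** The strongest reply is that the documents never say the windows are fixed to Day 0. The target days may be a nominal schedule drawn for a second dose on Day 112, and the labels point to the actual infusion. Section 11.5.2 also refers to the 8-week visit by time since the final dose. A Day-0 reading puts a contact meant to follow the infusion before it, which counts against that reading. Handling of delayed doses and documentation of out-of-window visits are left to the Study Specific Procedures, which are not available here. This stands to the extent that the Day-0 anchor is the literal reading and not an express rule. It does not remove the problem: Section 9.9 names Appendix L as the source of the windows, Appendix I uses the same day scale, and neither document states a moving anchor.

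A reader might infer three stronger points, which the documents do not support.

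- **Correctly timed samples are discarded as a rule.** Section 6.4.4.1 says only that out-of-window specimens may be excluded. The per-protocol wording in Section 6.4 concerns when product is received, and a dose on Day 126 is in window. No exact-interval sample is lost when infusion #2 is within its target window. Secondary analyses use actual collection and dosing times when necessary.
- **Safety follow-up could precede the infusion.** Visit 8 is a phone contact without specimens (Appendix G, footnote 16). Section 9.8 and Appendix I, footnote 3, tie solicited-event collection to the infusion itself, and Appendix I also marks solicited-event assessment at Visit 9. No safety consequence follows.
- **The primary estimates lose much precision.** Step 6 shows otherwise, even with the full allowable windows in use. If both visits keep to their target windows (infusion ±7, visit ±3), Visit 9 spans only 46–66 days.

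**Conclusion.** The point holds as an error in the table: labels, target days and windows for Visits 8–11 cannot all be followed unless infusion #2 is on Day 112, and neither document states the anchor. Applied literally, Visit 9 covers 35–77 days, and for second doses more than 7 days from Day 112 the exactly timed sample is the one that may be dropped from the primary concentration analysis. The possible exclusion rests on the specimen rule in Section 6.4.4.1, which is written for concentrations; the mislabelling of time affects the neutralization summaries as well.

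The ranges are date arithmetic and need no assumption beyond the literal reading. The precision figures assume uniform timing and exponential decline, and they are small. How many participants would be affected depends on how often infusion #2 is given outside Days 105–119, which the documents do not forecast. The table should be corrected, preferably before the primary concentration and neutralization data are analysed, but the matter does not put the trial's objectives at risk.

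**What to change.** In Appendix L (Part B), define Visits 8, 9, 10 and 11 as the actual infusion #2 date plus 4, 56, 112 and 168 days, with the windows now printed, and mark the present day numbers as nominal for a second dose on Day 112. The window for infusion #2 itself need not change. In the SAP, state that window checks and summaries after infusion #2 use time since the actual infusion #2. SAP Section 1 already expects later revisions to add analyses beyond safety, so the sentence can go there. If the Study Specific Procedures already re-anchor the visits, the protocol table should say the same.

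The cost is a table edit, a change to the visit calendar in the database and one SAP sentence. No visits or samples are added.

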1 OVERVIEW

The following describes the Statistical Analysis Plan (SAP) for the analysis of data from HVTN 140 for Safety Monitoring Board (SMB) reports, the Final Study Report (FSR) for Safety, Protocol Team (PT) reports for immunogenicity data, and the FSR for Immunogenicity. As detailed in SCHARP SOP-0013, Revision 5 (effective date: August 15, 2016), this SAP is required prior to the first analysis and must be approved by the lead protocol statistician. SMB reporting begins shortly after enrollment opens, and subsequent revisions are expected to describe analysis of immunogenicity data. The SAP will be reviewed prior to the first SMB report and before the final analysis with all major revisions of the plan archived.

2 PROTOCOL SUMMARY

A phase 1 dose-escalation clinical trial to evaluate the safety, tolerability, and pharmacokinetics of PGDM1400LS alone and in combination with VRC07-523LS and PGT121.414.LS in healthy, HIV-uninfected adult participants

Study Products

- **PGDM1400LS:** a human mAb that targets the HIV-1 V2 glycan, centered on N160. It is a derivative of PGDM1400 that was engineered to improve *in vivo* elimination half-life. It has been developed by the Vaccine Research Program (VRP) of the National Institute of Allergy and Infectious Diseases (NIAID). PGDM1400LS was manufactured under current Good Manufacturing Practice (cGMP) standards at Just-Evotec (Seattle, Washington) under contract to DAIDS's Vaccine Translational Research Branch (VTRB). The drug product was filled and released at the VRC Pilot Plant, operated under contract by Vaccine Clinical Materials Program (VCMP), Leidos Biomedical Research, Inc., Frederick, MD. The drug product is provided at 100 mg/mL as 10 mL glass vials with a 4.75 mL fill volume.
- **PGT121. 414.LS:** is a human mAb that targets the HIV-1 V3 glycan, centered on N332. It is a derivative of PGT121 that was engineered for improved manufacturing, stability and *in vivo* elimination half-life by Just Biotherapeutics in collaboration with [name] and Collaboration for AIDS Vaccine Discovery (CAVD) investigators. The drug substance was manufactured under cGMP standards at Just Biotherapeutics under contract to DAIDS's VTRB. The drug product was filled and released by the VRC and VCMP, Leidos Biomedical Research, Inc., Frederick, MD. Product is provided at 100 mg/mL as 10 mL glass vials with a 4.75 mL fill volume.
- **VRC-HIVMAB075-00-AB (VRC07-523LS):** is a human mAb that targets the HIV-1 CD4 binding site. It was developed by the VRC/NIAID/NIH and manufactured under cGMP standards at the VRC Pilot Plant operated under contract by the VCMP, Leidos Biomedical Research, Inc., Frederick, MD. Product is provided at 100 ± 10 mg/mL as 10 mL glass vials with a 6.25 ± 0.1 mL fill volume and 3 mL glass vials with a $2.25 \text{ mL} \pm 0.1 \text{ mL}$ fill volume.

Participants

- About 95 healthy, HIV-1-uninfected volunteers aged 18 through 50 years

Study arm	N*	Dose	Route	Month 0	Month 4
Part A					
Group 1	3	5 mg/kg	IV	PGDM1400 LS	-
Group 2 ¹	3	20 mg/kg	IV	PGDM1400 LS	-
Group 3 ¹	3	20 mg/kg	SC	PGDM1400 LS	-
Group 4 ²	3	40 mg/kg	IV	PGDM1400 LS	-
Group 5 ²	3	40 mg/kg	SC	PGDM1400 LS	-
Part B**					
Group 6 ³	16	20 mg/kg + 20 mg/kg + 20 mg/kg	IV	PGDM1400 LS + VRC07- 523LS + PGT121.414. LS	PGDM1400 LS + VRC07- 523LS + PGT121.414. LS
Group 7 ³	16	20 mg/kg + 20 mg/kg + 20 mg/kg	SC	PGDM1400 LS + VRC07- 523LS + PGT121.414. LS	PGDM1400 LS + VRC07- 523LS + PGT121.414. LS
Group 8 ³	16	1.4 g + 1.4 g + 1.4 g	IV	PGDM1400 LS + VRC07- 523LS + PGT121.414. LS	PGDM1400 LS + VRC07- 523LS + PGT121.414. LS
Group 9 ³	16	1.4 g + 1.4 g + 1.4 g	SC	PGDM1400 LS + VRC07- 523LS + PGT121.414. LS	PGDM1400 LS + VRC07- 523LS + PGT121.414. LS
Group 10 ⁴	16	40 mg/kg + 40 mg/kg + 40 mg/kg	IV	PGDM1400 LS + VRC07- 523LS + PGT121.414. LS	PGDM1400 LS + VRC07- 523LS + PGT121.414. LS
Total		95			

IV = intravenous infusion; SC = subcutaneous infusion; *additional participants may be enrolled to ensure the availability of safety data from at least 3 participants in each group; **antibodies will be administered sequentially as 3 separate infusions; + sign = "and".

¹Opening enrollment in Groups 2 & 3 follows review of safety data for participants in Group 1. Details are described in Section 11.3.1.

²Opening enrollment in Group 4 & 5 follows review of safety data for participants in Groups 1- 3.

³Opening enrollment in Groups 6, 7, 8, and 9 follows review of safety data for participants in Part A.

⁴Opening enrollment in Group 10 follows review of safety data for participants from Groups 1-9.

3 OBJECTIVES AND ENDPOINTS

3.1. Primary objective:

Primary objective 1:

To evaluate the safety and tolerability of PGDM1400LS when administered via intravenous (IV) or subcutaneous (SC) routes (Part A) and of PGDM1400LS, VRC07-523LS and PGT121.414.LS when administered in sequence IV or SC (Part B)

Primary endpoints 1:

- Local and systemic Solicited AEs, laboratory measures of safety, Unsolicited AEs, and SAEs
- Early discontinuation of administration and reason(s) for discontinuation and early study termination

Primary objective 2:

To evaluate the serum concentrations and pharmacokinetics of PGDM1400LS after a single administration (Part A) and of PGDM1400LS, VRC07-523LS, and PGT121.414.LS after each three-mAb administration (Part B)

Primary endpoint 2:

Serum concentrations of PGDM1400LS, VRC07-523LS and PGT121.414.LS at prespecified timepoints among participants who received all scheduled product administrations

Primary objective 3:

To evaluate the individual mAb-specific serum neutralizing activity after single product administration of PGDM1400LS (Part A) and after each three-mAb administration of PGDM1400LS, VRC07-523LS and PGT121.414.LS (Part B)

Primary endpoint 3:

Magnitude and breadth of neutralizing activity measured with Env pseudotyped viruses specific for either PGDM1400LS, VRC07-523LS or PGT121.414.LS in TZM-bl cells at prespecified timepoints among participants who received all scheduled product administrations

3.2. Secondary objective:

Secondary objective 1:

To correlate serum concentrations of PGDM1400LS, VRC07-523LS and PGT121.414.LS with corresponding virus neutralization titers in serum

Secondary endpoints 1:

- Serum concentrations of PGDM1400LS, VRC07-523LS and PGT121.414.LS at prespecified timepoints for all participants in all groups regardless of how many product administrations and how much product they received
- Magnitude of serum neutralizing activity measured with mAb-specific Env-pseudotyped viruses in TZM-bl cells at prespecified timepoints for all participants in all groups regardless of how many product administrations and how much product they received

Secondary objective 2:

To determine whether the mAbs maintain their expected combined magnitude and breadth of serum neutralizing activity after each PGDM1400LS, VRC07-523LS and PGT121.414.LS three-mAb administration (Part B) as predicted by the known magnitude and breadth of neutralization of the corresponding mAb combinations as non-infused clinical products

Secondary endpoint 2:

Magnitude of neutralizing activity against a panel of Env-pseudotyped reference viruses that are sensitive to all three bnAbs in TZM-bl cells at selected timepoints for all participants in all groups regardless of how many product administrations and how much product they received

Secondary objective 3:

To determine whether anti-drug antibodies (ADA) are present

Secondary endpoint 3:

ADA titers in each group measured at prespecified timepoints for all participants in all groups regardless of how many product administrations and how much product they received

Secondary objective 4:

To evaluate the impact of body weight and other baseline covariates on the pharmacokinetics of PGDM1400LS, VRC07-523LS and PGT121.414.LS in both the weight-based and fixed-dose groups.

Secondary endpoint 4:

Serum concentrations of PGDM1400LS, VRC07-523LS and PGT121.414.LS at prespecified timepoints

3.3. Exploratory objective:

Exploratory objective 1:

To determine whether any confirmed positive ADA samples have functional activity that impacts the neutralizing activity of PGDM1400LS, VRC07-523LS and PGT121.414.LS

Exploratory objective 2:

To further evaluate non-neutralizing anti-viral activities, additional assays (eg, ADCC, ADCP, virion capture) may be performed for activities that the PGDM1400LS, VRC07-523LS and PGT121.414.LS are shown to exhibit in vitro

Exploratory objective 3:

To conduct analyses related to predicting serum neutralization over time against a set of potentially exposing viruses in a future efficacy trial for ranking and down-selecting bnAb regimens

Exploratory objective 4:

To conduct analyses related to furthering the understanding of HIV, passive immunity, immunology, vaccines, and clinical trial conduct.

4 COHORT DEFINITION

Participants

About 95 healthy, HIV-1-uninfected volunteers aged 18 through 50 years

Design

Multicenter, randomized, open-label study

Duration per participant

6 months per participant in Part A and 10 months per participant in Part B of scheduled clinic visits

Estimated total study duration

14 months (includes enrollment, planned safety holds, and follow-up)

5 POTENTIAL CONFOUNDERS

Characterization of the safety of the vaccine is susceptible to confounding by adverse events not related to the vaccine that by chance occur more often in one arm of the trial than another. Therefore analyses involving adverse events will incorporate the reported relationship to product as assessed by HVTN staff.

6 RANDOMIZATION

There will be no randomization for Group 1 as they will be enrolled first. Contingent on safety data from Group 1, Groups 2 and 3 will be randomized and enrolled simultaneously. Contingent on safety data from Groups 2 and 3, Groups 4 and 5 will be randomized and enrolled simultaneously. Contingent on data from Part A, Groups 6, 7, 8, and 9 will be randomized in blocks to ensure balance across groups for simultaneous enrollment. There will be no randomization for Group 10. A participant's randomization assignment will be computer generated and provided to the CRS pharmacist through a web-based randomization system.

7 BLINDING

Participants and CRS staff will be unblinded to participant treatment arm assignments. Laboratory Center staff will be unblinded to whether a sample is from Part A or Part B, but will remain blinded to treatment assignment within Part A or Part B during sample analysis.

8 STATISTICAL ANALYSIS

All safety data from enrolled participants will be analyzed according to the initial randomization assignment regardless of how many study product administrations and how much study product they received. Analyses of safety data are modified intent-to-treat (MITT) in that individuals who are randomized but not enrolled do not contribute data and hence are excluded. Because of the brief length of time between randomization and enrollment—typically no more than 4 working days—very few such individuals are expected.

The primary analysis of mAb concentration and anti-viral functional activity data are per-protocol (PP) in that only individuals who receive the expected mAb at the expected dose level within the expected visit window contribute data. Secondary analysis will also involve the MITT cohort, and when necessary account for the actual specimen collection time, and the actual time and dose amount of each product administration.

Analyses for primary endpoints will be performed using SAS and R. Additional software may be used to perform non-compartmental PK and population PK analyses (eg, Monolix). All other descriptive and inferential statistical analyses will be performed using SAS, StatXact, or R statistical software.

No formal multiple comparison adjustments will be employed for multiple primary or secondary endpoints. However, multiplicity adjustments will be made for certain primary or secondary endpoint assays, as discussed below, when the assay endpoint is viewed as a collection of hypotheses (eg, testing multiple pseudo-viruses to determine a positive antiviral functional activity response). Unless otherwise noted, all statistical tests will be 2-sided and will be considered statistically significant if $p < 0.05$.

